### 10.5 Outcome Data

Death within the 6-week follow-up period?	
 
• Yes
 
• No
 
 
If Yes:
 
 
• Date of death: dd/mm/yyyy
 
• In ICU at time of death? Yes/No
 

Discharged within the 6-week follow-up period?	
 
• Yes
 
• No
 
 
If Yes:
 
 
• Date of discharge: dd/mm/yyyy
 
• Destination of discharge: 
 
○ Transfer to another hospital
 
○ Transfer to a rehabilitation unit
 
○ Usual place of residence/Home
 
○ Absconded
 
○ Other (specify _____)
 
 
 

Was the patient admitted to intensive care at any point during the 6-week follow up period?	
 
• Yes
 
• No
 
 
If Yes:
 
 
• Date of admission to ICU: dd/mm/yyyy
 
• Was the patient discharged from ICU during the 6-week follow up period? Yes/No
 
 
If Yes:
 
 
• Date of discharge from ICU: dd/mm/yyyy
 

Was the patient intubated during admission?	
 
• Yes
 
• No
 

Did the patient require a tracheostomy?	
 
• Yes
 
• No
 

Was the patient requiring ventilatory support at time of death/the end of the 6-week follow up period (whichever event occurs first)?	
 
• Yes
 
• No
 

Did any adverse events of special interest occur in the 6-week follow-up period? (Select all that apply)	
 
• None
 
• Pressure Ulcer
 
• Pneumonia
 
• Pulmonary embolism
 
• Deep venous thrombosis
 
• Decubitus Ulcer
 

	
 
• Urinary tract infection
 
• Symptomatic haematoma
 
			
Did any surgical site infections occur in the 6-week follow-up period?	
 
• Yes
 
• No
 
 
If Yes:
 
 
• Required antibiotics only
 
• Required debridement
 
• Required removal of metalwork
 
			
Did the patient return to the operating theatre for spinal surgery during the current admission?	
 
• Yes - planned
 
• Yes - unplanned
 
• No
 
 
If Yes: Was the re-operation at:
 
 
• Same level
 
• Different level
 
			
Did the patient survive to the end of the follow up period (6 weeks post-admission or until they were discharged from hospital, whichever came first)?	
Yes No
 
Was the patient still an inpatient at the end of 6 weeks post-admission?
 
- Yes - No
			
Frankel Grade at the end of the 6-week follow up period or at time of death/discharge (whichever event occurs first)?	
 
• A: Complete motor and sensory loss
 
• B: Complete motor loss, incomplete sensory loss
 
• C: Incomplete motor loss without practical use
 
• D: Incomplete motor loss, able to ambulate with or without walking aids
 
• E: Free of neurological symptoms
 
			
How independent is the patient in the following activities of daily living at the end of the follow up period or at time of discharge?		Unaided	With Aid	Completely Dependent
	Feeding			
	Grooming			
	Bathing			
	Dressing – upper body			
	Dressing – lower body			
	Toileting			
	Swallowing			
	Bladder management			
	Bowel management			
	Transfers			
Climbing stairs				
What is the patient using to mobilise at the end of the follow up period or at time of discharge (whichever event occurs first)?	
 
• Mobilising independently
 
• Use of one walking stick / crutch
 
• Use of two walking sticks / crutches
 
• Use of a frame
 
• Wheelchair
 
• Not mobilising (bed-bound)
 
			

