### *Management of traumatic spinal injury (TSI)*

Delays in the initiation of comprehensive management of TSI have been shown to add to the complexity of management, result in a higher incidence of complications, longer hospitalisation, added costs and poor outcomes. The Lancet Commission on Global Surgery estimates that 5 billion people worldwide lack access to safe, affordable, accessible surgical care and this disparity extends to neurosurgical interventions. Challenges to delivering emergency management of TSI in LMICs are often compounded by inadequate pre-hospital care, lack of infrastructure and trained manpower.

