### 3.4 Duration of Study

Local study teams may pick any 30-day period between the 6-month study period to conduct the study. Teams must follow patients for up to 6-weeks post-admission or until they are discharged or die (whichever event occurs first). For example, if a team selects 1/6/2021 as their start date, they must include all patients who meet the inclusion criteria between 1/6/2021 and 30/6/2021. Moreover, if a patient is admitted during the inclusion period on 30/6/2021 they should be followed up until the 11/8/2021 or until discharge or death (whichever event occurs first).

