### Outcome Data

Outcomes will be measured up to 6-weeks or until death/discharge (whichever event occurs first). This follow-up period was selected after consultation with experienced clinicians from high and low HDI settings to balance the aim of capturing significant short-term outcome events with practicalities of robust data collection across centres. This is supported by literature suggesting that over half of patients are typically lost to follow-up, with significantly increased barriers to follow-up in LMICs, and that early outcomes assessed within shorter time frames, particularly in these settings, remain significant and useful. A range of outcomes after traumatic spinal injury will be assessed including:

- Frankel grade at 6-weeks post-admission (or at discharge, whichever event occurs first). This has been demonstrated as a feasible measure to collect in both high and low resource settings.
- 6-week mortality
- Length of stay (LOS)
  - Hospital
  - Intensive Care Unit
- Perioperative complications (where applicable)
  - Return to operating theatre during follow-up period
  - Surgical site infection (SSI)
  - Adverse events of special interest e.g. pressure ulcer, pneumonia, deep venous thrombus
- Functional status at 6-weeks or discharge
  - Independence with activities of daily living
  - Mobility

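### Surgical site infection is an undated Yes/No over a window that starts at admission, so crude comparisons by HDI group or site mix infection risk with post-operative observation time; return to theatre has two conflicting windows and no date

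*Combined protocol and SAP*

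**What the plan says.** Section 3.4 sets the clock: "Teams must follow patients for up to 6-weeks post-admission or until they are discharged or die". Its worked example says that "if a patient is admitted during the inclusion period on 30/6/2021 they should be followed up until the 11/8/2021". The Outcome Data part of section 3.5 repeats the rule ("Outcomes will be measured up to 6-weeks or until death/discharge (whichever event occurs first") and lists surgical site infection (SSI) and return to theatre as perioperative complications. None of these sections defines a window that starts at the operation.

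Appendix 10.5 collects SSI through "Did any surgical site infections occur in the 6-week follow-up period". The answer is Yes or No, with the treatment required if Yes, and no date.

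Return to theatre is described in section 3.5 as "Return to operating theatre during follow-up period". The form in 10.5 asks instead "Did the patient return to the operating theatre for spinal surgery during the current admission". The form records whether the return was planned and at which level, but not when it happened.

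The operation date is in 10.4, which is completed only when surgery took place at the participating institution. Dates of death and of discharge within the 6-week period are in 10.5.

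Section 5 plans to analyse outcomes, including adverse events, by HDI group in nested models, and to compare sites with a median odds ratio. It does not mention post-operative time observed. Section 6 does not list it as a limitation.

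**The concern.** An SSI or a re-operation can arise only after an operation, yet the observation period is counted from admission. Two patients with the same infection risk can be observed for very different lengths of time after surgery, depending on when they were operated on and when they left hospital. Both are likely to differ between centres, and variation in operative management between centres and HDI settings is what the study sets out to describe.

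If SSI proportions are compared by HDI group or site without regard to observation time, part of any difference reflects how long patients were watched. A median odds ratio between sites would count that part as variation between sites. Because SSI carries no date, the events cannot later be placed in a common post-operative window.

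For return to theatre the problem is more basic. Two sites could apply different windows and both be following the documents.

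**Working it through.** **The plan's own figure.** From 30/6/2021 to 11/8/2021 is 42 days, so the worked example in section 3.4 agrees with six weeks from admission.

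**Observation after surgery.** For surgery on day *d* after admission and a post-operative stay of *L* days, observed days = min(42 − *d*, *L*), cut shorter by death. The ceiling 42 − *d* is 40 days for surgery on day 2, 21 for day 21 and 7 for day 35. It binds only when *d* + *L* > 42. In that case each day of delay removes one day of observation. Otherwise observation equals the post-operative stay, whatever the day of surgery.

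**Illustration of size.** The documents give no SSI rate, onset time, surgical delay or length of stay, so all of these are assumptions. Take equal true risk and exponential onset after surgery with median *m* days. The share recorded in *t* days is 1 − 2^(−*t*/*m*). For surgery on day 2 versus day 21:

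| Median onset | Nobody leaves before day 42 (40 vs 21 days) | 28-day stay (28 vs 21 days) | Stay of 21 days or less |
|---|---|---|---|
| 7 days | 0.875/0.981 = 0.89 | 0.875/0.938 = 0.93 | 1 |
| 14 days | 0.646/0.862 = 0.75 | 0.646/0.750 = 0.86 | 1 |
| 21 days | 0.500/0.733 = 0.68 | 0.500/0.603 = 0.83 | 1 |

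**A different onset shape.** With a true risk of 10% and lognormal onset (sigma 0.6, median 14 days), if all patients stay to day 42 the recorded SSI is 9.6% for surgery on day 1 and 5.0% for day 28. If all leave 10 days after surgery it is 2.9% for both. Timing then makes no difference, but most infections are missed.

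**Direction.** Suppose one site operates on day 2 with a 10-day post-operative stay, and another on day 21 with a 21-day stay. They observe 10 and 21 days. With exponential onset and median 14 days, the ratio of late to early is 0.646/0.390 = 1.66. At equal risk, the late site now looks worse.

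**Would an offset of post-operative days repair it?** An offset assumes a constant event rate. In the first column of the table (40 versus 21 days), the late-to-early ratio of events per observed day is:
- median 7 days: (0.875/21)/(0.981/40) = 1.70
- median 14 days: (0.646/21)/(0.862/40) = 1.43
- median 21 days: (0.500/21)/(0.733/40) = 1.30

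True risk is equal throughout, so the offset turns a bias in favour of late surgery into one against it.

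**Return to theatre.** The two windows differ for anyone still an inpatient after day 42. For those patients 10.5 records no discharge date, because that date is requested only for discharge within the 6-week period. The end of the admission-based window is then unknown, and without a re-operation date the answers cannot be cut back to day 42.

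**The case against.** The strongest reply has five parts.

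1. The day-42 cap matters only for patients whose stay would pass it. For stays of 10 or 14 days after surgery, operations on any day from 1 to 28 get identical observation. This stands, and it limits the timing effect to long-stay patients. It does not remove the problem, since discharge then determines observation time and may also differ between sites.

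2. The return-to-theatre field has no 6-week limit. Read literally, late surgery does not shorten its window. This stands. For that outcome the defect is the conflict between section 3.5 and Appendix 10.5, together with the missing date.

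3. Section 5 never commits to a crude SSI proportion. It does not name SSI, and reading its adverse events to include SSI is an inference from the outcome list. It plans nested random-effects models and correction for explanatory features, and the main analysis is descriptive. This stands in part. Adjustment is possible, but observation time is not named, and no model can restore an event date that was not collected.

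4. The validator in section 4.2 records operation dates from theatre logs over 10 weeks. These might date some re-operations. They are meant for validation, their use as outcome data is not described, and they do not help with SSI.

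5. A reader might infer that late-operating centres will look safer, and that this hides the harm of delay described in the Background, where delays "result in a higher incidence of complications". The documents do not support that. The Background sentence concerns delay in starting comprehensive management, not time to surgery specifically. Differences in post-operative stay can also outweigh or reverse the effect.

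**Conclusion.** The point holds for SSI as a problem of unequal and unrecorded observation time. As written, crude comparisons by HDI group or site would mix infection risk with the length of post-operative observation. Patients whose stay would pass day 42 lose one observed day for each day that surgery is delayed. For those discharged earlier, observation equals the post-operative stay.

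Neither the size nor the net direction can be fixed from the documents. The range 0.89 to 0.68 is an upper-end illustration. It assumes equal true risk, exponential onset with a median of 7 to 21 days, all surgery on day 2 at one site and day 21 at the other, and nobody leaving or dying before day 42. It shrinks to 1 once post-operative stays are 21 days or less.

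For return to theatre, the conflict between section 3.5 and Appendix 10.5 needs no assumption and must be reconciled.

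The descriptive primary aim is not threatened. The change is worth making because it is cheap and because missing SSI dates cannot be repaired from the data set after collection.

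**What to change.** **Appendix 10.5.** Add the date of first SSI and the date of first return to theatre. Reconcile the return-to-theatre wording in section 3.5 and 10.5 to a single window.

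**Section 5.** State that SSI and return to theatre will be analysed among patients operated on at the participating institution, the only ones with an operation date. Estimate cumulative incidence from the operation date, censored at the earlier of admission + 42 days and discharge, with death as a competing event. Report post-operative days observed by HDI group and site alongside the estimates. Do not rely on an offset of post-operative days.

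**Section 6.** State that discharge may be informative censoring, since patients who leave early may differ in infection risk, and that infections after discharge are not captured.

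**Cost.** Two date fields, completed only for patients with an event, one reconciled definition and a few sentences of analysis text. Operation, death and in-window discharge dates are already collected for these patients.

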### 3.5 Study measures

The following categories of routine clinical data will be collected prospectively for all patients included in the study. The full data set is included in *Appendix A*.

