#### Initial injury and admission data

- Baseline demographics e.g. age, gender
- Type and mechanism of injury
- Pre-hospital timeline, transfers and transportation
- Clinical presentation on arrival to hospital e.g. GCS, Kampala Trauma Score, Frankel grade
- Initial injury details
- Admission details

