## **5. Statistical Analysis**

Anonymised data will be analysed by the central study team. Fundamentally the main analysis will consist of a quantitative description of case-mix and the variations in processes of care. Identification and description of areas where known best practice is lacking or unavailable will be performed. This will enable identification of potential targets for future implementation studies.

In addition, early outcomes will be assessed to identify case-mix and process factors that may form a substrate for intervention. Participating centres will be stratified based on their country into groups based on their Human Development Index (HDI). The Human Development Index is calculated for each country based on its life expectancy at birth, years of schooling and gross national income (GNI) per capita.

Specifically, after data validation and curation, the primary analysis will comprise of (1) statistical descriptive analysis of patient-level registry variables, (2) characterisation of processes of care using statistical descriptions of both provider profiling data and patient-level process variables followed by a description of typical process groupings. This will follow and extend methodologies that have previously been applied successfully to traumatic brain injury. Case-mix and process analysis will be stratified in a nested way by site, country, and association with human development index (HDI).

Analysis for the secondary objectives will consist of a quantitative statistical summary of non-operative and operative management. Intra- and inter-site variances will be compared and associations with HDI and process of care factors sought.

Whilst only short-term outcomes can be obtained in this pragmatic point-study, outcomes analysis will be attempted for early mortality, functional status as assessed using the 5-point Frankel Grade, neurology, adverse events and trajectory from admission to 6 weeks post-injury (or discharge or death, whichever occurs first). These will be analysed by HDI group in an appropriate nested model accounting for random effects of site and country. Either ordinal models (for statistical power) or dichotomised models will be used depending on the statistical properties of the data and suitability of model assumptions. Mixed effects models will be used to assess the relationship between HDI and deterioration in functional status at 6 weeks while controlling for confounding variables.

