	
 
● Motor Response 
 
○ Obeys commands - 6
 
○ Localising pain - 5
 
○ Withdrawal from pain - 4
 
○ Flexion to pain - 3
 
○ Extension to pain - 2
 
○ No motor response - 1
 
 
 

Kampala Trauma Score	
 
● Age 
 
○ 5-55
 
○ <5 or >55
 
 
 
● SBP (mmHg) 
 
○ >89
 
○ 50-89
 
○ 1-49
 
○ Undetectable
 
 
 
● Respiratory rate (/min) 
 
○ ≤9
 
○ 10-29
 
○ ≥30
 
 
 
● Neurological status 
 
○ Alert
 
○ Responds to verbal stimuli
 
○ Responds to painful stimuli
 
○ Unresponsive
 
 
 
● Serious injuries 
 
○ None
 
○ 1
 
○ 2 or more
 
 
 

Frankel Grade at initial assessment	
 
● A: Complete motor and sensory loss
 
● B: Complete motor loss, incomplete sensory loss
 
● C: Incomplete motor loss without practical use
 
● D: Incomplete motor loss, able to ambulate with or without walking aids
 
● E: Free of neurological symptoms
 

Major intracranial injury (defined as requiring hospital admission in its own)	
 
● Yes
 
● No
 

Site of PRIMARY spinal cord injury	
 
● Occipital condyle to S1:
 
● Unknown
 

Primary vertebral fracture Level	
 
● Occipital condyle to S1:
 
● Unknown
 

Deformity	
 
● Yes
 
● No
 

Any other injury (can select multiple)	
 
● Chest
 
● Abdomen
 
● Pelvis
 
● Long bones
 

Admission location	
 
● General wards
 
● HDU
 
● ITU
 

Admitting Team	
 
● Orthopaedics
 
● Neurosurgery
 
● General Surgery
 
● Medicine
 
● Emergency Department
 

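### ADL and mobility have no pre-injury reference and comorbidity is not recorded, so HDI comparisons of function cannot separate earlier dependence from the effect of the injury

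*Combined protocol and SAP*

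**What the plan says.** Section 3.5 (Outcome Data) lists "Functional status at 6-weeks or discharge", made up of ADL independence and mobility. Appendix A 10.5 collects these with two items. The first is "How independent is the patient in the following activities of daily living at the end of the follow up period", covering eleven activities at three levels. The second is "What is the patient using to mobilise at the end of the follow up period or at time of discharge", with six levels. Neither item has a pre-injury or admission counterpart.

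Neurological grade is handled differently. Appendix A 10.1 has "Frankel Grade at initial assessment" and 10.5 has "Frankel Grade at the end of the 6-week follow up period or at time of death/discharge", so Frankel change can be computed.

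The patient-level baseline in section 3.5 begins with "Baseline demographics e.g. age, gender" and goes on to injury details and the acute state on arrival (GCS, Kampala Trauma Score, Frankel grade). Section 5 plans mixed effects models to "assess the relationship between HDI and deterioration in functional status at 6 weeks while controlling for confounding variables", without listing the confounders. It also plans a median odds ratio comparison of sites, corrected for explanatory features found in the descriptive work. In the same section the Frankel grade is named as the measure of functional status. Section 6 (Limitations) does not mention pre-injury status.

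**The concern.** A patient who walked with a frame before the injury and one who needs a frame because of it get the same mobility code. Likewise, a patient already dependent for bathing or stairs is recorded as a dependent outcome of TSI. If such patients are more common in one HDI group, that group's functional results look worse even when the injury and the care have the same effect everywhere. Depending on direction, a real difference could instead be hidden.

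The missing comorbidity item reaches further. Describing case-mix is the primary objective (section 1.1), and comorbidity is a plausible confounder of early mortality and adverse events, which section 5 also analyses by HDI group. Differences between sites in pre-injury health can also appear as between-site variation in the median odds ratio. A covariate that was never collected cannot be adjusted for.

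**Working it through.** **Step 1: field check.** The plan states no sample size, outcome rate or effect size, so there is no figure to reproduce. Reading Appendix A field by field:

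- 10.1: date of birth, gender, injury type and energy, mechanism, transport, GCS, Kampala score, initial Frankel grade, intracranial and other injuries, admission details. These cover demographics, the injury and the acute state.
- 10.2 to 10.4: imaging, management, operation.
- 10.5: outcomes, including ADL and mobility once each. Discharge destination is recorded, but not where the patient lived before.

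There is no item on pre-injury mobility, pre-injury ADL, comorbidity, frailty or ASA grade. The provider profiling questionnaire is not reproduced, but section 3.2 describes it as institution-level (caseload, catchment, frameworks, resources), so it would not supply patient baselines.

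**Step 2: which analyses are exposed.** ADL and mobility have one value each, so neither change nor deterioration can be computed. Frankel grade has two values. A stable old deficit sits in both and adds no change, although it can limit the grade a patient can reach.

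**Step 3: size of the bias, on assumed inputs.** Let p be pre-injury dependence and q the risk of new dependence among those previously independent. Assume the already dependent stay dependent. Observed dependence is o = p + (1 − p)q. With the same q in both groups, the false difference is (p₁ − p₂)(1 − q). All values of p and q are assumptions.

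With q = 0.30:

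| p, group 1 vs group 2 | o, group 1 vs group 2 | False difference (points) | Crude odds ratio |
|---|---|---|---|
| 15% vs 5% | 40.5% vs 33.5% | 7.0 | 1.35 |
| 25% vs 5% | 47.5% vs 33.5% | 14.0 | 1.80 |
| 35% vs 5% | 54.5% vs 33.5% | 21.0 | 2.38 |
| 5% vs 2% | 33.5% vs 31.4% | 2.1 | 1.10 |
| 10% vs 3% | 37.0% vs 32.1% | 4.9 | 1.24 |
| 20% vs 5% | 44.0% vs 33.5% | 10.5 | 1.56 |

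First row: 0.15 + 0.85 × 0.30 = 0.405 and 0.05 + 0.95 × 0.30 = 0.335; (0.405/0.595) ÷ (0.335/0.665) = 1.35. For the last three pairs, letting q run from 0.20 to 0.50 gives false differences of 1.5 to 12.0 points. With an assumed 300 patients per group, a two-sided 0.05 test and clustering ignored, those three rows would be declared significant about 8%, 24% and 75% of the time.

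**Step 4: equal pre-injury dependence.** The false difference is then zero and a true difference is diluted. Take true new dependence of 20% versus 30% (odds ratio 1.71). With p = 5%, 10% or 20% in both groups, the 10-point difference becomes 9.5, 9.0 or 8.0 points, and the odds ratio 1.60, 1.51 or 1.40.

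**Step 5: adjustment for collected fields.** Suppose dependence follows age only: 1% in younger and 20% in older patients, with 50% older in one group and 15% in the other. Then p is 10.5% versus 3.85%, and the crude false difference is 0.0665 × 0.70 = 4.7 points. Within age strata it is zero, and age is collected.

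**The case against.** The strongest reply is that section 5 takes functional status to mean the Frankel grade, which has an initial value. A reader might infer that the planned deterioration and recovery analyses lack a baseline. On section 5's own definition they do not. That stands, with two qualifications: comorbidity may still confound the Frankel analyses, and section 3.5 gives functional status a different meaning (ADL and mobility), so the two sections need reconciling.

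Second, the odds ratios in the working are crude, while the plan adjusts. Age, standing-height falls, road-traffic categories and injury energy are all collected, and these describe the most obvious case-mix contrast between settings. Patients with an earlier eligible TSI admission are excluded (section 3.1.2.2), which removes one source of old deficit. This also stands. A reader might infer that every HDI comparison of function is distorted; the documents give no prevalences from which to show that, and the bias remaining after adjustment is unknown.

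Third, the primary objective is descriptive and short-term outcomes are secondary. That lowers the priority of the functional comparisons, but it does not answer the comorbidity gap in the case-mix description.

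Finally, recall of pre-injury function may itself differ by setting. That is a real cost of the remedy.

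**Conclusion.** The gap holds for ADL, mobility and comorbidity. Pre-existing dependence cannot be separated from an outcome of TSI, and comorbidity cannot enter the case-mix description or the HDI and median-odds-ratio models. The resulting bias depends on how far pre-injury dependence differs by HDI group after adjustment for what is collected. On assumed inputs the crude spurious odds ratio runs from 1.10 to 2.38 at 30% new dependence. It is 1.00 if age explains the difference and is adjusted for, and equal prevalence only dilutes a true effect. The direction is not known from the documents.

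Two stronger readings are not supported. One is that this must be corrected for the study to meet its aims: the functional contrasts are secondary and the adjusted bias is not established. The other is that the missing baseline could never be retrieved: records carry an ORION identifier, and the documents do not say whether sites keep a local link. This is a cheap, worthwhile improvement.

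**What to change.** Add three items to Appendix A 10.1, asked of the patient or family, and test them in the pilot planned in section 4.1:

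1. Pre-injury mobility, on the six-level list already used in 10.5.
2. Pre-injury ADL independence: unaided, with aid, or dependent.
3. One comorbidity item, for example ASA grade.

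In section 5, adjust ADL and mobility comparisons for the pre-injury value and include comorbidity in the case-mix covariates of the HDI and median-odds-ratio models. State one meaning of functional status across sections 3.5 and 5, or name the Frankel, ADL and mobility analyses separately.

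If collection has closed, state the limitation in section 6. Report ADL and mobility contrasts by HDI as descriptive, adjusted for age, mechanism and initial Frankel grade. Add a sensitivity analysis that recovers new dependence as q = (o − p)/(1 − p) over a range of assumed p in each group. For example, 44.0% with p = 20% and 33.5% with p = 5% both return 30%.

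The cost is three form fields, a short addition to section 5, about a minute per patient, and recall error that may differ by setting.
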